2.5. Pooling Algorithm for Analysis Centers

Country is a randomization stratification factor and will be used as a factor in the analysis of the primary efficacy endpoint.

Countries within a geographical region (as defined by the United Nations Statistics Division [<http://unstats.un.org/unsd/methods/m49/m49regin.htm#ftnb>]) with fewer than 12 subjects in the intent-to-treat (ITT) analysis set (see Section 2.6.1.1 below) across all sites within the country will be combined to form a single pooled ‘country’ for analysis.

If only one country within a geographical region has fewer than 12 ITT subjects, it will be combined with the next smallest country within the geographical region.

If the combination of all countries within a geographical region totals fewer than 12 ITT subjects, that geographical region will be combined with an appropriate country from a neighboring geographical region.

As of the cessation of randomization, the following countries had fewer than 12 randomized, treated subjects: Canada (n = 7), Mexico (n = 9), Germany (n = 8), Finland (n = 7), and Italy (n = 3). For analysis purposes, Canada and Mexico will be combined with USA (n = 188) and Germany, Finland, and Italy will be combined to form a single EU pooled ‘country’.

Unless otherwise noted, the use of ‘country’ in this document refers to pooled countries as defined in this section.

2.6. Analysis Sets

2.6.1. Efficacy Analysis Sets

2.6.1.1. Primary Efficacy Analysis Set

The primary efficacy analysis set includes all randomized subjects (intent-to-treat [ITT] analysis set).

2.6.2. Safety Analysis Set

The safety analysis set includes all randomized subjects with at least one dose of study medication.

2.6.3. Pharmacokinetics Analysis Set

The pharmacokinetics (PK) analysis set is defined as subjects who have received at least one dose of study medication and have at least one valid blood sample drawn for PK analysis.

2.6.4. Biomarker Analysis Sets

The CSF A β analysis set includes all randomized subjects with valid CSF A β data at baseline and at ≥ 1 post-baseline visit. All CSF A β values will be blindly reviewed for qualification.

The amyloid PET analysis set includes all randomized subjects with valid amyloid PET data at baseline and at ≥ 1 post-baseline visit.

The CSF p-tau and t-tau analysis set includes all randomized subjects with valid CSF p-tau and t-tau data at baseline and at ≥ 1 post-baseline visit.

The tau PET analysis set includes all randomized subjects with valid tau PET data at baseline and at ≥ 1 post-baseline visit.

2.7. Definition of Subgroups

The primary efficacy endpoint and adverse events will be summarized based on the following subgroups:

- Sex (male, female)
- Race (White, Black or African American, Asian, or Other)
- Age Group (<65 years, 65 to 74 years, ≥ 75 years)
- Education level
- Country (per Section 2.5)
- Disease stage: Stage 1, 2, or 3 based on the criteria below:

	Amyloid positive	Baseline hippocampal volume < median baseline hippocampal volume	Baseline ^a RBANS Total Scale <85
Stage 1	Yes	No	No
Stage 2	Yes	Yes	No
Stage 3	Yes	Yes	Yes

^a RBANS assessment performed 5 to 10 days before randomization.

3. INTERIM ANALYSIS AND DATA MONITORING COMMITTEE REVIEW

An independent, external Data Monitoring Committee (DMC) has been established to perform safety monitoring over the entire duration of the study and review interim analysis results for futility. An independent, external statistical support group (SSG) will perform the interim efficacy analysis and provide statistical reports to the DMC. Of the interim analyses planned in the protocol, only the futility interim analysis of $A\beta_{1-40}$ in CSF was performed because of the cessation of screening, randomization, and dosing.

Details of the DMC and its procedures are provided in the DMC Charter¹. The names, roles, and contact information of the members of the Janssen R&D Sponsor Committee (SC) are also available in the DMC charter. Additional details about the timing of the interim analyses and the flow of information between the DMC, SSG, SC, JRD, and other involved parties is provided in an operational plan ([Attachment 1](#)). Note, the operational plan is no longer in effect due to the early cessation of the study.

3.1. Safety Monitoring

The DMC will conduct safety monitoring meetings approximately every 3 months over the entire duration of the study. The content of the safety monitoring reports is specified in the DMC Charter.

3.1.1. Interim Analyses of $A\beta_{1-40}$ in CSF

An unblinded interim analysis of $A\beta_{1-40}$ in CSF will be performed by the SSG and DMC.

The IA for CSF $A\beta_{1-40}$ will take place when at least 20 subjects per group (60 total subjects) in the CSF $A\beta_{1-40}$ analysis set (Section 2.6.4) meet the following criteria:

- The subject has a Month 12 CSF $A\beta_{1-40}$ result.
- The subject was $\geq 85\%$ compliant with treatment through the Month 12 visit.
- The subject was dosed for ≥ 6 of the 7 days prior to the Month 12 visit.

Justification for this sample size is provided in Attachment 2.

If the proportion of subjects meeting the treatment compliance criteria is low, the IA will be repeated including all subjects with a biomarker result at the specified time point. In this case, the Sponsor Committee will take both sets of results into account to make a final decision.

There will be no Type I error adjustment for the interim analysis since superiority will not be declared.

Tables summarizing data will have columns A, B and C randomly representing the study treatments ‘Placebo’, ‘Atabecestat 5 mg’ and ‘Atabecestat 25 mg’. Subjects randomized to the atabecestat 10 mg group before implementation of Amendment 3 will be included in the atabecestat 5 mg group.

Demographics and APOE $\epsilon 4$ carrier status will be summarized as described in Section 4.1.1 and Section 4.1.2. Subject disposition, treatment compliance, and extent of exposure will be summarized as described in Section 4.2, Section 4.3, and Section 4.4, respectively.

The objective of this IA is to assess the treatment effect on CSF $A\beta_{1-40}$. Since screening, randomization, and dosing has been stopped, the DMC will not make a recommendation to the JRD Sponsor Committee, but will report the results to the JRD Sponsor Committee.

The following endpoints will be analyzed:

- Key endpoint: Percent change from baseline to Month 12 in CSF $A\beta_{1-40}$.
- Supportive endpoint: Percent change from baseline in plasma $A\beta_{1-40}$.

Absolute values, changes from baseline and percent changes from baseline in $A\beta_{1-40}$ in CSF and plasma will be summarized by time point and treatment group using descriptive statistics (mean, standard deviation, median, range, and 95% CI).

Percent changes from baseline in $A\beta_{1-40}$ in CSF and plasma at Month 12 will be analyzed based on an analysis of covariance (ANCOVA) model that includes treatment group and the baseline value as a covariate. The Least Squares (LS) means and treatment differences versus placebo with the corresponding 95% confidence intervals will be provided.

The criterion for lack of effect on $A\beta_{1-40}$ in CSF is based on the LS mean difference (A-P) in percent reduction from baseline in $A\beta_{1-40}$ between the 25 mg dose (A) and placebo (P):

- If $(A - P) < 50\%$, then conclude lack of effect for atabecestat
- If $(A - P) \geq 50\%$, then do not conclude lack of effect for atabecestat

Where P is the LS mean for percent reduction versus baseline in $A\beta_{1-40}$ in the placebo group, and A is the LS mean for percent reduction versus baseline in $A\beta_{1-40}$ in the 25 mg group.

4. SUBJECT INFORMATION

The ITT analysis set and the safety analysis set will be used throughout this document. The number of subjects screened and the number of subjects in each analysis set will be summarized by treatment group and overall. In addition, the distribution of subjects by region, country, and site will be presented. Region is defined as found at <http://unstats.un.org/unsd/methods/m49/m49regin.htm>.

4.1. Demographics and Baseline Characteristics

4.1.1. Demographics

Table 2 presents a list of the demographic variables that will be summarized by treatment group and overall for the ITT analysis set.

Table 2: Demographic Variables

Continuous Variables	Summary Type
Age, years	Descriptive statistics (N, mean, standard deviation [SD], median and range [minimum and maximum])
Weight, kg	
Height, cm	
Body Mass Index (BMI), kg/m^2	
Categorical Variables	
Age (<65years, 65 to 74 years, ≥ 75 years)	Frequency distribution with the number and percentage of subjects in each category
Sex (male, female)	
Race ^a (American Indian or Alaska Native, Asian, Black or African American, Native Hawaiian or other Pacific Islander, White, Other, Multiple)	
Ethnicity (Hispanic or Latino, Not Hispanic or Latino, Not Reported, Unknown)	
BMI (underweight <18.5 kg/m^2 , normal 18.5-<25 kg/m^2 , overweight 25-<30 kg/m^2 , obese ≥ 30 kg/m^2)	

^a If multiple race categories are indicated, then Race is recorded as “Multiple.”

4.1.2. Baseline Characteristics

Previous study participation

Subjects who had previously participated in the Janssen non-interventional studies REGISTRYALZ0001 (CHARIOT-PRO) or 54861911ALZ0001 (study to evaluate psychometric comparability of translated, culturally adapted versions of the PACC components with the US English versions) could participate in the current study. The number and percentage of subjects who previously participated in these studies will be summarized by treatment group and overall.

APOE ε4 carrier status

The APOE genotype and the number and percentage of subjects who are APOE ε4 carriers will be summarized by treatment group and overall.

Hippocampal volume

Left and right hippocampal volume will be derived from MRI. For each subject, the average of the left and right volumes will be calculated. Baseline left, right, and average hippocampal volume will be summarized with descriptive statistics by treatment group and overall.

Family history of dementia

The number and percentage of subjects with at least one first degree family member, at least one second degree family member, or either a first- or second-degree family member diagnosed with dementia will be summarized by treatment group and overall, with additional summaries for each type of dementia (mixed, Alzheimer's, vascular, Lewy body, unknown, or other).

Marital status and education level

The number and percentage of subjects in each marital status category (single, separated, married, divorced, widowed) and in each category of highest education level completed (less than upper secondary/high school, upper secondary/high school, some education after upper secondary/high school, bachelor's degree or equivalent, master's degree or equivalent or higher) will be summarized by treatment group and overall.

4.1.3. Medical History and Baseline General Physical Examination

The verbatim terms used in the CRF by investigators to identify medical history diseases or conditions will be coded using the Medical Dictionary for Regulatory Activities (MedDRA). For each disease/condition, the number and percentage of subjects with at least 1 past occurrence and with at least 1 ongoing occurrence of the disease or condition will be summarized by treatment group and overall.

For each general physical examination body system, the number and percentage of subjects with an abnormal finding will be summarized by treatment group and overall. A listing of specific physical examination abnormalities will be provided.

A listing of pre-planned surgeries or procedures including the specific surgery/procedure, the planned date of the surgery/procedure, and the study day of the planned surgery/procedure will be provided.

4.1.4. Informant characteristics

[Table 3](#) presents a list of the informant characteristics that will be summarized by treatment group and overall for the ITT analysis set.

Table 3: Informant Characteristics

Continuous Variable	Summary Type
Age, years	Descriptive statistics (N, mean, standard deviation [SD], median and range [minimum and maximum])
Categorical Variables	
Sex (male, female)	Frequency distribution with the number and percentage of subjects in each category
Relationship to subject (spouse or partner, sibling, child, cousin, friend, paid companion, other)	
Does informant live with the subject? (yes, no)	

4.1.5. Rosen-modified Hachinski Ischemic Scale (MHIS)

The MHIS is an 8-item clinical questionnaire which evaluates items and characteristics typical of vascular dementia¹⁵. It is collected during screening only. Abrupt onset, history of strokes, focal neurological symptoms, and focal neurological signs are scored as 2 if present and 0 if absent. Stepwise deterioration, somatic complaints, emotional incontinence, and history of hypertension are scored as 1 if present and 0 if absent. A MHIS total score is calculated as the sum of the 8 individual item scores. Item scores are recorded on an electronic device which will provide the total score.

For each item or characteristic, the number and percentage of subjects rated as having the item or characteristic (rated as ‘present’) will be summarized by treatment group and overall. The MHIS total score will be summarized with descriptive statistics by treatment group and overall.

4.1.6. Geriatric Depression Scale (GDS)

The GDS is a 30-item measure used to identify depression in elderly individuals²³. The 30-item GDS is collected during screening only. Each item is answered ‘yes’ or ‘no’ and scored as 0 or 1 according to the table in [Attachment 3](#). The GDS-30 total score is the sum of the 30 individual item scores. Item scores are recorded on an electronic device which will provide the total score.

The GDS-30 total score will be categorized as follows:

- Normal (GDS-30 total score ≤ 9)
- Mildly Depressed (GDS-30 total score 10 to 19)
- Severely Depressed (GDS-30 total score ≥ 20)

The GDS-30 total score will be summarized with descriptive statistics by treatment group and overall and the number and percentage of subject in each GDS-30 total score category will also be summarized by treatment group and overall.

4.1.7. Assessment of Psychological Well Being

The Assessment of Psychological Well Being is composed of the 15-item short version of the Geriatric Depression Scale (GDS-15) and the 6-item short version of the State-Trait Anxiety Inventory (STAI). See Section [6.4.1](#) for additional details. The total scores of each scale during screening will be summarized with descriptive statistics by treatment group and overall.

4.1.8. Amyloid Status

At screening, amyloid status will be evaluated in all subjects using either CSF amyloid β_{1-42} ($A\beta_{1-42}$) concentrations or brain amyloid burden by PET imaging or both. Study eligibility will be determined by a positive result showing evidence of elevated accumulation on either evaluation.

For subjects with results of both biomarkers at screening, a cross-tabulation of elevated amyloid accumulation status (positive or negative) between the 2 biomarkers will be provided to evaluate concordance.

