**Evidence of elevated amyloid accumulation (Step IV)** will be assessed by either (1) a CSF sample for determination of A $\beta$ 1-42 concentration or (2) an amyloid PET scan for determination of cerebral fibrillar amyloid. Subjects can have both CSF collection and amyloid imaging performed (the aim is that approximately 20% of subjects will have both screening biomarker evaluations to better understand concordance of the biomarkers in screening and treatment). Amyloid status for study entry will be based on at least 1 of these biomarkers confirming elevated amyloid accumulation. It is sufficient to demonstrate elevated amyloid accumulation by 1 of the 2 markers, but the decision to perform 1 or both needs to be made before either result is available. The amyloid disclosure visit will be performed when both results, if applicable, are available. Subjects with negative results for both biomarker tests of elevated amyloid accumulation cannot be rescreened. Subjects who elect up front to be tested on only 1 of the biomarkers cannot be screened for the other if their results are negative, unless the decision is made before either result is available.

All subjects who undergo the **Step IV** amyloid burden assessment will have their results disclosed during a separate in-clinic **amyloid status disclosure visit** conducted during the screening period by a clinical investigator approved for this role. This visit must take place at least 2 days prior to the baseline cognitive assessments. Disclosure of the amyloid accumulation results will be per local laws and regulations. Informant attendance is not required at this visit, but may be permitted if the subject agrees. Subject concern about developing AD and his/her views and perceptions of amyloid imaging, as well as perception of future time, will be repeated following disclosure of amyloid status using the questionnaires specified above for Step I. The Impact of Events Scale (IES) will be administered over the phone (or at a visit) within 3 days following the amyloid status disclosure visit.

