4.2. Disposition Information

Screened subjects and reason for screen failures will be summarized overall.

The number of subjects in the following disposition categories will be summarized throughout the study by treatment group and overall:

- Subjects randomized
- Subjects receiving study medication
- Subjects completing the study
- Subjects who discontinued study medication
- Reasons for discontinuation of study medication
- Subjects who terminated study prematurely
- Reasons for termination of study

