6.3. Electrocardiogram (ECG)

ECGs will be performed at screening; at randomization; after randomization at Month 1, Month 3, and Month 6; then, every 6 months through Month 54 (or early termination).

The ECG variables that will be analyzed are heart rate, PR interval, RR interval, QRS interval, QT interval, and QTc using the following correction methods:

- Bazett's formula: $QTcB \text{ (msec)} = QT \text{ (msec)} / (60/HR(\text{bpm}))^{1/2}$;
- Fridericia's formula: $QTcF \text{ (msec)} = QT \text{ (msec)} / (60/HR(\text{bpm}))^{1/3}$;
- Linear Derived formula: $QTcLD(\text{msec}) = QT(\text{msec}) + \beta * (1-60/HR(\text{bpm}))$, where β is the estimated slope derived from the linear regression model $QT(\text{msec}) = \alpha + \beta * 60/HR(\text{bpm})$ using all observations prior to treatment initiation of all subjects excluding screen failures;
- Sagie formula: $QTcI \text{ (msec)} = QT(\text{msec}) + 154 * (1 - 60/HR(\text{bpm}))$

QTcB and QTcF will be provided by the central ECG vendor and not recalculated. Triplicate ECGs, completed within a 4-minute time period, are collected at each visit. The value for each parameter on a given date will be the average of the values obtained from the triplicate ECGs.

Descriptive statistics will be presented by treatment group for the above ECG variables at each scheduled time point and for the on-treatment endpoint. Change from baseline to each scheduled on-treatment time point and to the on-treatment endpoint will be descriptively summarized by treatment group. For off-treatment visits, change from the off-treatment baseline (see Section 2.4) will also be calculated.

The number and percentage of subjects with treatment-emergent potentially clinically important ECG values as defined in [Table 5](#) below will be presented for each on-treatment time point by treatment group.

Table 5: Potentially Clinically Important (PCI) Criteria for Selected ECG Parameters

Parameter	Criteria for Low PCI Values	Criteria for High PCI Values
HR	< 50	> 100
PR	< 120	> 200
QRS	< 70	> 120
QT		> 500

The number and percentage of subjects with corrected QT values within each of the categories defined below will be presented for the maximum post-baseline, on-treatment value and for each on-treatment time point by treatment group.

- QTc Interval:
 - Males
 - ≤ 450 msec
 - > 450 to ≤ 480 msec
 - > 480 to ≤ 500 msec

- >500 msec
- Females
 - ≤ 470 msec
 - >470 to ≤ 500 msec
 - >500 msec
- QTc change from baseline
 - ≤ 30 msec

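### Does the CSF-by-PET concordance table in SAP 4.1.8 need a named analysis set, given that randomised subjects cannot be negative on both markers?

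*SAP*

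**What the plan says.** SAP Section 4.1.8 explains that amyloid status is assessed at screening by CSF, by PET or by both, and then gives the entry rule: "Study eligibility will be determined by a positive result showing evidence of elevated accumulation on either evaluation". For subjects who had both tests, "a cross-tabulation of elevated amyloid accumulation status (positive or negative) between the 2 biomarkers will be provided to evaluate concordance". It does not say whether subjects who failed screening are counted, and it names no percent agreement or kappa.

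The opening of SAP Section 4 says: "The ITT analysis set and the safety analysis set will be used throughout this document". Both sets hold randomised subjects only. Section 2.6.1.1 states "The primary efficacy analysis set includes all randomized subjects (intent-to-treat [ITT] analysis set"), and Section 2.6.2 states "The safety analysis set includes all randomized subjects with at least one dose of study medication".

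Other parts of the SAP do deal with people who were never randomised. Section 4.2 says "Screened subjects and reason for screen failures will be summarized overall", and the QT correction in Section 6.3 is fitted "using all observations prior to treatment initiation of all subjects excluding screen failures".

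Protocol Section 9.1.2 gives the reason for dual testing. The aim is that "approximately 20% of subjects will have both screening biomarker evaluations to better understand concordance of the biomarkers in screening and treatment". The same section, like Protocol Section 4, bars subjects negative on both tests from rescreening.

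**The concern.** A programmer who applies the Section 4 sentence literally would tabulate randomised subjects. Nobody negative on both markers can be randomised, so one of the four cells would be empty because of selection, whatever the true concordance. Negative agreement would be 0% by construction, and overall agreement would be understated.

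That matters a little because the protocol pays for dual testing in order to learn about concordance. Section 3.2.6.1 of the protocol also justifies the either-marker entry rule by saying the two measures agree well enough. A table distorted by selection could appear to contradict that premise.

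**Working it through.** The plan states no concordance figure, so there is nothing to reproduce. The check has two parts: what happens under the restrictive reading, and which reading the text supports.

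**Effect of restricting to randomised subjects**

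Let *a* be the share positive on both markers, *b* and *c* the two discordant shares, and *d* the share negative on both.

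- Overall agreement, all dual-tested: (a + d)/(a + b + c + d).
- Overall agreement, randomised only (d = 0): a/(a + b + c).
- Difference: d(b + c)/[(a + b + c)(a + b + c + d)]. This is above zero whenever there are double negatives and any discordance.
- Agreement given a positive result, for example a/(a + b), does not contain *d*, so the amyloid rule leaves it unchanged.

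The direction is therefore fixed, but the size needs rates that the documents do not give. For illustration, assume the same proportion *p* positive on each marker, discordance split equally, and no other selection between testing and randomisation. With p = 0.35 and true agreement 0.85:

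- discordant = 1 − 0.85 = 0.150
- both positive = 0.35 − 0.150/2 = 0.275
- both negative = 1 − 0.150 − 0.275 = 0.575
- overall agreement, randomised only = 0.275/(0.275 + 0.150) = 64.7%, against 85.0%
- positive agreement = 0.275/0.35 = 78.6% in either set
- negative agreement = 0.575/0.65 = 88.5% in all tested, 0% in randomised only

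Overall agreement in randomised subjects, over a range of assumptions:

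| Positive on each marker | True 80% | True 85% | True 90% |
|---|---|---|---|
| 25% | 43% | 54% | 67% |
| 35% | 56% | 65% | 75% |
| 50% | 67% | 74% | 82% |
| 65% | 73% | 79% | 86% |

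The understatement runs from 4 points (90 − 86) to 37 points (80 − 43). If the 20% aim held among the 557 randomised (SAP Section 1), about 0.20 × 557 = 111 subjects would be in the restricted table.

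**Which population the text supports**

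- Section 4.1.8 starts from everyone evaluated at screening and only then states how eligibility is decided. At that point those who will test negative are still in the group.
- The cross-tabulation sentence carries its own definition, possession of both results at screening. A specific population ordinarily overrides a general statement.
- The neighbouring baseline sections (4.1.1 to 4.1.7 and 4.1.9) present results by treatment group and overall. Section 4.1.8 does not, which fits a table containing people who have no treatment group.
- The Section 4 sentence does not say that the two sets are used exclusively, and the sentence after it counts subjects screened.
- Section 6.3 excludes screen failures in so many words, which suggests that the authors did not regard them as excluded automatically.
- The protocol's stated purpose covers concordance in screening as well as in treatment. Only the screened population serves the first.

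**The case for a change.** The strongest case for a change is that the two readings give materially different tables and the text does not choose between them. The Section 4 sentence is broad, and a programmer could follow it in good faith. The protocol requires the choice of one test or both to be made before either result is known, so all dual-tested screenees form the natural concordance sample, and restricting to randomised subjects would waste that safeguard. One sentence would settle it, using results that already exist because they decided eligibility.

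Much of this stands. The population is unstated, the algebra is right, and the cost of clarifying is small. The textual signals are also not conclusive. In particular, the missing reference to treatment group is only suggestive, because Section 4 attaches that phrase even to the sentence that counts screened subjects.

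What does not stand is the step from an unstated population to a misleading result. That needs the less natural reading and also someone to compute an overall percentage or a kappa that the SAP does not plan. A plain two-by-two table with nobody in the double-negative cell, placed after a rule requiring at least one positive, shows its own limitation.

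**Conclusion.** No change to the plan is called for. Section 4.1.8 leaves out a detail, and its wording, the rest of the SAP and the protocol's purpose all point an analyst to the sensible choice: every screened subject with both results, including those who failed screening.

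Should a randomised-only table be produced instead, it would still give valid positive agreement, provided no other exclusion between testing and randomisation is related to the results. Overall and negative agreement should not be read from it. The downward direction of overall agreement is certain whenever double negatives and discordance exist. The size is not known for this trial: the 4 to 37 points above rest wholly on assumed rates, equal positivity on both markers and no other selection.

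The stakes are small either way. Concordance is not among the primary, secondary or exploratory objectives. The table is one descriptive item among the baseline characteristics of a trial whose stated objectives, by SAP Section 1, can no longer be evaluated. No efficacy or safety conclusion depends on it.
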